5.5 Clinic Visit (End of Week 4)

Subjects will visit the clinic at the end of Week 4 at a time specified by the clinic. The following procedures will take place during this visit:

- Verification that inclusion and exclusion criteria have not been violated since last visit
- UB cigarette documentation for subjects assigned to continue smoking UB cigarettes
- Urine drug and alcohol screens
- Vital signs
- Urine pregnancy test for females
- Review of AEs and concomitant medication use.
- Return canister with used cigarette butts for counting
- Completion of subjective effects questionnaires
- Dispense new canister for collecting used cigarette butts during next ambulatory period
- Review smoking and nicotine product use restrictions
- Test product dispensing for the following ambulatory period

5.6 End-of-Study (End of Week 6 Visit or on Early Discontinuation)

At the end of the study, the following procedures will be performed:

- Review of AEs and concomitant medication use.
- Vital signs
- Body weight
- 12-lead ECG
- Clinical chemistry, hematology and urinalysis
- Symptom-driven physical examination, if applicable
- Provide smoking cessation information

5.7 Follow-Up Call

The CRU will attempt to contact all subjects who participated in the study (including subjects who terminate the study early) using their standard procedures approximately 7 days after the last contact. This will be to:

- Review AEs and concomitant medication use

- Provide smoking cessation information

A symptom-driven physical examination may also be required, in which case subjects will return to the clinic for this to take place.

5.8 Confinement

Subjects will check in to the clinic at the end of Weeks, -1, 2 and 6, at times specified by the clinic. Subjects will be housed until after the 24-hour urine collection, nicotine PK assessment, puffing topography and other study procedures.

5.9 Tobacco Product Use

Except as required by the protocol, consumption of tobacco- or nicotine-containing products will not be permitted during the entire duration of the study from the start of Week -1 through discharge from the study. During the baseline period, subjects will be asked to confine their smoking to one brand which will be deemed their UB. While in the CRU during 24-hour confinement periods, cigarette consumption will be tracked by the number of products dispensed.

5.10 Product Trial

At screening, subjects will have an opportunity to smoke 2-3 VLN cigarettes over a 1-hour period to ensure that they can tolerate smoking those cigarettes for a period of 6 weeks. The number of cigarettes smoked will be documented, as will any abnormal events (e.g., excessive coughing) during the product trial. Subjects who react negatively (*i.e.*, unwilling to use and/or cannot tolerate the product [experience adverse events (AEs) that will prevent them from continuing to use the product as judged by the Investigator]) to the VLN cigarettes during the product trial period will not continue in the study.

5.11 Meals

Standard meals and snacks will be served at appropriate times as determined by the clinic during confinement. Meals each day should be provided at similar times. One approximately 250 ml, caffeinated beverage will be allowed to be taken with each meal. During confinement, water will be allowed *ad libitum* and subjects will be encouraged to maintain their usual hydration habits.

5.12 Study Assessments

All study assessments will take place at the times noted in the [Summary of Study Events](#) tables above unless otherwise noted below.

5.12.1 Medical History/Demographic Data/Record of Concomitant Medication

Self-reported medical history and socio-demographic data, including name, sex, age (each subject must show proof of age with government-issued identification [e.g., driver's license or Verified Clinical Trials]), race, ethnicity, address, and phone number will be recorded at Screening for each subject.

Medical history will include any clinically significant neurological, gastrointestinal, renal, hepatic, cardiovascular, psychiatric, respiratory, metabolic, endocrine, hematological or other major disorders. Medical history is defined as any condition that started prior to Screening and ended prior to the product trial. A concomitant disease is any disease that started prior to, and which was still ongoing at Screening.

Any concomitant medications taken from 30 days prior to Screening through discharge will be recorded in the CRF and source documents.

5.12.2 Tobacco/Nicotine Product Use History

Subjects will be required to report previous tobacco- and nicotine-product use histories to satisfy the study inclusion and exclusion criteria. In addition, the subject will be asked if he/she is planning to quit smoking within the next 3 months. Those planning to quit will be excluded from participating in the study.

The subject's tobacco use and smoking history (including a color photocopy of their UB cigarette package along with a ruler) will be recorded at Screening. Verification of the subject's UB cigarette brand will be made at the end of Week -1 clinic visit.

5.12.3 Urine collections for BoE Assessments

Urine will be collected over 24-hour periods for urine BoE measurements, during the clinic visits at the end of Weeks, -1, 2 and 6. Creatinine in urine will also be measured and used to report BoE as amount per unit of creatinine.

Prior to the first urine sample collection, each subject will be instructed as to the urine collection methods. All urine during an interval is to be collected and subjects will be asked to empty their bladder before the start of the urine collection period.

The urine samples collected during a single 24-hour period will be pooled together and weighed. The pooled samples will be thoroughly mixed before providing aliquots for analyses. A separate document will be provided for handling and processing of the samples.

The total weight of all urine collected over each 24-hour period will be documented. Urine aliquots will be prepared within 60 minutes from removal of the pooled collection from the refrigerator and then stored at approximately -20°C pending analysis, according to the table below:

Analyte	Volume per aliquot	Number of aliquots
Total NNAL	10ml	2
Total NNN	10ml	2
T _{neq}	10ml	2

3-HPMA	10ml	2
S-PMA	10ml	2
1-OHP	10ml	2
Creatinine	10ml	2

5.12.4 Blood sampling for BoE assessments

Blood samples for COHb in whole blood and cotinine in plasma will be collected via direct venipuncture at the scheduled visits as delineated in the [Summary of Study Events Tables](#). Samples will be collected at approximately 13:00, following the subject's lunchtime meal, and will be preceded by at least a 30-minute abstention from study product use.

Samples for COHb will be collected into two 4 ml sodium heparin vacutainers. Immediately following collection, the blood samples will be inverted gently to mix between 8 and 10 times. The whole blood samples will be stored at 5°C (± 3°C) until analyzed by the Celerion Bioanalytical Laboratory (Lincoln, Nebraska).

Samples for plasma cotinine will be collected into a 4 ml plastic K₂EDTA (lavender top) vacutainer tube. Immediately following the collection, blood samples will be gently mixed by inverting the tubes 8 times. The samples may be kept at ambient temperature prior to centrifuge, and will be centrifuged at 1000 - 1300 RCF for 10 minutes at 5°C within 60 minutes of collection. After centrifugation, approximately 1 ml of plasma will be transferred using into 2 appropriately labeled 3.5 ml polypropylene screw top tubes.

Samples will then be stored at approximately -20°C within 120 minutes of collection and until analyzed by Celerion Bioanalytical Services (Lincoln, Nebraska). Samples will be analyzed using a validated analytical method with the appropriate quality controls in accordance with FDA Good Laboratory Practice (GLP) regulations (Title 21 Code of Federal Regulations [CFR] Part 58).

Approximately 36 ml of blood will be required for blood BoE assessments during the entire study.

Additional instructions for collection, processing, and shipping of blood BoE samples will be provided separately.

5.12.5 Puffing topography measurements

At clinic visits at the end of Weeks -1, 2 and 6, a randomly-selected subset of 18 non-menthol and 18 menthol smoker subjects will complete a puffing topography evaluation session with either their UB (Week -1) or the VLN (Weeks 2 and 6) cigarettes. These subjects will be/have been assigned to switch to smoking VLN cigarettes. These assessments will only be performed at a single clinical site (Lincoln) and will take place during the 24-hour confinement period.

During the puffing topography assessment, subjects will engage in a 1-hour *ad libitum* smoking session with their UB (Week -1) or the VLN (Weeks 2 and 6) cigarettes. In these sessions, subjects will smoke cigarettes with the mobile smoking puff analyzer (SPA-M; Sodim). The topography device will be monitored to ensure the device is actively recording during each session.

Topography assessment will be started at least one hour following either the subject's breakfast or lunch. The puffing topography session for each subject at Weeks 2 and 6 should be within \pm 2 hours of the time of their Week -1 session.

Additional details and instructions for puffing topography procedures will be provided separately.

The following topography parameters will be assessed:

- Puff duration
- Puff volume
- Peak puff flow rate
- Average flow rate
- Inter-puff interval

5.12.6 Blood sampling for nicotine PK assessments

At clinic visits at the end of Weeks -1, 2 and 6, a randomly-selected subset of 12 non-menthol and 12 menthol smoker subjects will complete a nicotine pharmacokinetic assessment session with either their UB (Week -1) or the VLN (Weeks 2 and 6) cigarettes. These subjects will be/have been assigned to switch to smoking VLN cigarettes and will be selected from the subjects who undergo topography assessment. These assessments will only be performed at a single clinical site (Lincoln) and will take place on the morning following the 24-h confinement period.

Following the completion of the 24-hour urine collection period, selected subjects will remain in the clinic for a further night, in which they will abstain from smoking any cigarettes/using any nicotine-containing products for at least 12 hours prior to the PK assessment session. During this session, subjects will smoke a single cigarette *ad libitum* during a 5-minute period. A 4 ml blood sample for plasma nicotine analysis will be drawn into a plastic K2-EDTA (lavender top) vacutainer tube at -5, 2, 5, 7, 10, 12, 15, 30, 45, 60, 90, 120, 150 and 180 minutes relative to the start of cigarette smoking, as delineated in the [Summary of Study Events Tables](#). In total, approximately 144 ml of blood will be drawn from each of the selected subjects during the entire study for nicotine pharmacokinetic analysis.

The blood samples collected for plasma nicotine analysis may be kept at room temperature prior to centrifugation, and will be centrifuged at approximately 1000-1300 RCF at \sim 5°C for approximately 10 minutes, within 60 minutes from collection. After centrifugation, the plasma will be transferred to two methanol prewashed 3.5 ml polypropylene screw cap tubes. Samples will then be stored at approximately -20°C within 120 minutes of collection and until analyzed by Celerion Bioanalytical Services (Lincoln, Nebraska).

Samples will be analyzed using a validated liquid chromatography coupled to tandem mass spectrometry detection analytical method with the appropriate quality controls in

accordance with FDA Good Laboratory Practice (GLP) regulations (Title 21 Code of Federal Regulations [CFR] Part 58).

Additional instructions for collection, processing, and shipping of samples for nicotine PK assessments will be provided separately.

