Puffing topography Data Parameters and Summarization	
Puffing topography will be measured in a randomly-selected subset of 18 non-menthol and 18 menthol cigarette smokers during an ad libitum usage session at the clinic visits at the end of Week -1 (UB cigarette) and Weeks 2 and 6 (VLN cigarettes). These subjects will be/have been assigned to switch to smoking VLN cigarettes. Puffing topography will be assessed using the mobile smoking puff analyzer (SPA-M; Sodim) during the confinement periods. Topography assessment will only be performed at one of the two clinical sites (Lincoln).
 
The following topography parameters will be assessed:
 
• Puff duration• Puff volume• Peak puff flow rate• Average flow rate• Inter-puff interval 
All data will be listed by subject and summarized using descriptive statistics.

Nicotine PK Data Parameters and Summarization	
Plasma nicotine levels will be assessed in a subset of 12 non-menthol and 12 menthol cigarette smokers before, during and after a 5-minute ad libitum smoking session with UB (Week -1) and VLN (Weeks 2 and 6) cigarettes. These subjects will be/have been assigned to switch to smoking VLN cigarettes and will be randomly selected from the subjects selected to undergo topography assessments. Blood samples will be drawn at -5, 2, 5, 7, 10, 12, 15, 20, 30, 45, 60, 90, 120, 150 and 180 minutes relative to the start of cigarette smoking a single cigarette. Nicotine PK assessment will be performed on the day following 24-hour confined urine collection and after an overnight abstinence from cigarette smoking.
 
Plasma nicotine PK parameters, Cmax, Tmax and AUC will be computed from the individual plasma concentrations.
 
Nicotine concentrations and PK parameters will be listed by subject and summarized by study product and sex using descriptive statistics.

Subjective Effects Data Collection and Summarization	
Measurement of subjective effects will be made during the clinic visits at Weeks -1, 2, 4 and 6, with the single administration of the Fagerström Test for Cigarette Dependence (FTCD), the Brief Questionnaire of Smoking Urges (QSU-Brief), the Minnesota Nicotine Withdrawal Scale - Revised (MNWS-R) and a perceived health risk scale.
 
All data will be listed by subject and summarized by time point using descriptive statistics.

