⁸ Standard physical examination including oral cavity and oropharynx. A symptom driven examination can be performed at other time, at Investigator or designee's discretion.

⁹ Symptom driven and if deemed necessary.

¹⁰ Symptom driven and if deemed necessary based on the follow-up call. Subjects will visit the clinic for this to take place.

¹¹ Body weight only at Start of Week -1

¹² Body weight only at end of study

STUDY EVENTS/ASSESSMENTS	Screening ¹	Clinic Visits					Out-of-CRU Between Clinic Visits		
		Start of Week -1	End of Week -1 (baseline)	End of Week 2	End of Week 4	End of Week 6			
Clinical Chemistry ¹³ , Hematology, Urinalysis	X							X	
Urine Drug and Alcohol Screen	X	X	X	X	X	X		X	
HIV, HBsAg, and HCV Serology	X								
Serum Pregnancy Test (females)	X								
Serum FSH Test ¹⁴	X								
Urine Cotinine Screen	X	X							
Exhaled CO Measurement	X	X							
Test Product (VLN cigarette) Trial	X								
Provide Smoking Cessation Information ¹⁵	X							X	X
Review of AEs	X ¹⁶	X	X	X	X	X		X	X
Urine Pregnancy Test (females)		X	X						
Review Restrictions on Smoking and Nicotine Product Use	X	X	X	X	X	X			
Reminder Contacts to return to the CRU ¹⁷		X ¹⁸					X ¹⁹		
Test Product Dispensing			X	X	X				

¹³ Clinical chemistry tests will be performed after at least an 8 hour fast; however, in case of dropouts or rechecks, subjects may not have fasted for 8 hours prior to the clinical chemistry sample being taken.

¹⁴ Postmenopausal females only

¹⁵ Subjects will be referred to the Quit Assist® website

¹⁶ AE recording to begin immediately after the product trial at Screening.

¹⁷ Phone calls or texts or instant messages (as per site preference) reminding subjects of clinic visits.

¹⁸ The day prior to clinic visit at start of Week -1 subjects will be contacted.

¹⁹The day prior to clinic visits at end of Weeks -1, 2, 4 and 6 subjects will be contacted.

STUDY EVENTS/ASSESSMENTS	Screening ¹	Clinic Visits					Out-of-CRU Between Clinic Visits		
		Start of Week -1	End of Week -1 (baseline)	End of Week 2	End of Week 4	End of Week 6			
Dispense Canisters for Used Cigarette Butt Collection		X	X	X	X				
Used Cigarette Butt Collection							X		
Used Cigarette Butt Canister Return			X	X	X	X			
24-hour Urine Collection for BoE analysis			X	X		X			
Plasma Sample for Cotinine Analysis			X	X		X			
Blood Sample for COHb Analysis			X	X		X			
Puffing Topography ²⁰			X	X		X			
Blood Samples for Nicotine PK Analysis ²¹			X	X		X			
Training on e-diary use		X							

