9. PHARMACOKINETIC ANALYSIS

9.1 Measurements and Collection Schedule

For a randomly-selected subset of 12 non-menthol and 12 menthol smoker subjects, PK blood sampling will occur following the completion of the 24-hour urine collection period on clinic visits at Weeks -1, 2, and 6. The selected subjects will remain in the clinic for a further night, in which they will abstain from smoking any cigarettes/using any nicotine-containing products for at least 12 hours prior to the PK assessment session. During this session, subjects will smoke a single cigarette (either their UB on Week -1 or the VLN on Weeks 2 and 6) *ad libitum* during a 5-minute period. Serial blood samples will be collected for plasma nicotine analysis at 5 minutes prior to and at 2, 5, 7, 10, 12, 15, 20, 30, 45, 60, 90, 120, 150, and 180 minutes relative to the start of cigarette smoking.

All concentration data will be included in the calculation of the individual PK parameters, the individual concentration-time plots (based on actual sample times), and in the mean concentration-time plots (based on nominal sample times). However, if there are any significant deviations from nominal sample times, some concentration data may be excluded from mean concentration-time plots and/or additional concentration-time plots of the mean data may be provided. All deviations and excluded data will be provided and discussed in the CSR.

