For the calculation of summary statistics, values that are below the limit of quantitation (BLQ) of <XX> are treated as 1/2 limit of quantitation.

. = Value missing or not reportable.

Notes for Generating the Actual Table:

Presentation of Data:

Concentrations will be presented to same precision as in bio data.

Summary statistics presentation with respect to the precision of the bioanalytical data: n = integer; Mean and Median +1; SD and SEM +2, Min and Max +0, CV% to 1 decimal. Summary statistics will be presented by sex and overall.

Programmer Note:

A row will be added above 'sample time' which will be labelled 'Week' and will have the following numbers: -1, 2, and 6
PK Time points are from Protocol: i.e. preproduct use and 2, 5, 7, 10, 12, 15, 20, 30, 45, 60, 90, 120, 150, and 180 minutes postproduct use
Note that 'sample time' is in 'min' not 'hr'

For Tables 14.2.7.3.1 through 14.2.7.4.2 the following footnote will be added if applicable: 'For the calculation of summary statistics, negative values are assigned a value of zero'

22nd Century Group, Inc
VLN Cigarettes
Celerion, Clinical Study Report No. CA24914

Table follows CPConcl template

Per study design needs, the following changes are made to this table relative to Celerion standard: columns <Product Sequence> and <Study Period> will be removed. Summary statistics will be presented by sex and overall.

Program: /CAXXXX/sas_prg/pksas/pk-conc-tables.sas DDMMYYYY HH:MM
Program: /CAXXXX/sas_prg/pksas/pk-conc-tables-sig.sas DDMMYYYY HH:MM
Program: /CAXXXX/sas_prg/pksas/adam_conc.sas DDMMYYYY HH:MM

Post-text Tables 14.2.7.5.1 through 14.2.7.10.2 will be in the following format:

Page 1 of X

Table 14.2.7.5.1 Baseline Adjusted Plasma Nicotine Pharmacokinetic Parameters Following Use of UB Non-Mentholated Filtered Cigarettes (Week -1) (Pharmacokinetic Population from PP)

Subject Number	param1 (units)	param2 (units)	param3 (units)	param4 (units)	param5 (units)	Parameters	
						param6 (units)	
X	XXX	X.XX	XXX	XXX	XX.X	X.XXX	
X	XX.X	X.XX	XXX	XXX	XX.X	X.XXX	
X	XXX	X.XX	XXX	XXX	XX.X	X.XXX	
X	XX.X	X.XX	XXX	XXX	XX.X	X.XXX	
X	XX.X	X.XX	XXX	XXX	XX.X	X.XXX	
X	X.XX	X.XX	XXX	XXX	XX.X	X.XXX	
X	XXX	X.XX	XXX	XXX	XX.X	X.XXX	
n	XX	XX	XX	XX	XX	XX	
Mean	XXX.X	X.XXX	XXX.X	XXX.X	XX.XX	X.XXXX	
SD	XX.XX	XX.XX	XX.XX	XX.XX	XX.XX	XX.XX	
CV%	XX.X	XX.X	XX.X	XX.X	XX.X	XX.X	
SEM	XX.XX	XX.XX	XX.XX	XX.XX	XX.XX	XX.XX	
Minimum	XX.X	X.XX	XXX	XXX	XX.X	X.XXX	
Median	XX.XX	X.XXX	XXX.X	XXX.X	XX.XX	X.XXXX	

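### Protocol 5.12.6 states about 144 ml of PK blood per subject, but its own 14-draw schedule gives 168 ml and the 15-draw schedule in the synopsis and SAP gives 180 ml; it also omits the 20-minute sample

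*Protocol*

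**What the plan says.** Protocol 5.12.6 describes PK sessions at the end of Weeks -1, 2 and 6 for 12 non-menthol and 12 menthol smokers. On volume per draw it says: "A 4 ml blood sample for plasma nicotine analysis will be drawn". Its sampling times run, with the first figure being minus 5, "5, 2, 5, 7, 10, 12, 15, 30, 45, 60, 90, 120, 150 and 180 minutes" from the start of smoking. That is 14 times, with nothing between 15 and 30 minutes. The paragraph closes with the total: "approximately 144 ml of blood will be drawn from each of the selected subjects".

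Three other places give a longer list:

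- The Nicotine PK entry in the protocol synopsis: "Blood samples will be drawn at -5, 2, 5, 7, 10, 12, 15, 20, 30, 45, 60, 90, 120, 150 and 180 minutes".
- SAP 9.1, after a sample 5 minutes before smoking: "2, 5, 7, 10, 12, 15, 20, 30, 45, 60, 90, 120, 150, and 180 minutes relative to the start of cigarette smoking".
- The programmer note in SAP 14.3 for Tables 14.2.7.1.1 through 14.2.7.4.2: "PK Time points are from Protocol: i.e. preproduct use and 2, 5, 7, 10, 12, 15, 20, 30, 45, 60", continuing to 180 minutes.

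Each of these has 15 times, including 20 minutes.

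Section 5.12.6 points to the Summary of Study Events Tables for the schedule. The row there, "Blood Samples for Nicotine PK Analysis", marks only the visits. Its footnote covers the subset, the site and the overnight abstinence. Neither gives sampling minutes.

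**The concern.** The volume per draw, the number of draws, the number of sessions and the total all stand in one section, and the total does not follow from the other three. The list of draws also disagrees with the synopsis of the same protocol and with the SAP.

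Two things are at stake. The first is the blood burden stated in a protocol that goes to the IRB, which is too low for the subjects who give the most blood. The second is site conduct. Section 5.12.6 is the procedures text, and staff who follow it literally would not draw at 20 minutes. The SAP concentration tables would then have a planned 20-minute column without data. Protocol 10.3 permits no deviations except in a medical emergency, yet taking the sample departs from 5.12.6 and omitting it departs from the synopsis.

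**Working it through.** **Inputs**

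- Volume per draw: 4 ml (Protocol 5.12.6).
- Sessions per subject: 3, at the end of Weeks -1, 2 and 6 (Protocol 5.12.6).
- Draws per session: 14 (Protocol 5.12.6), or 15 (synopsis, SAP 9.1, SAP 14.3 note). The only time that differs is 20 minutes.
- Stated total: 144 ml (Protocol 5.12.6).

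**Formula:** total = draws per session x ml per draw x sessions.

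**Attempt to reproduce the stated figure.** Working back, 144 / (4 x 3) = 12 draws per session. No section lists a 12-draw schedule. Other readings do not reach 144 either:

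| Reading | 14-time list | 15-time list |
|---|---|---|
| All draws, 3 sessions, 4 ml | 168 ml | 180 ml |
| Post-smoking draws only (13 or 14), 3 sessions, 4 ml | 156 ml | 168 ml |
| All draws, 2 sessions, 4 ml | 112 ml | 120 ml |
| All draws, 3 sessions, 3 ml | 126 ml | 135 ml |

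**Size of the gap**

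- 14 draws: 14 x 4 x 3 = 168 ml; 168 - 144 = 24 ml; 24 / 144 = 16.7%. Per session, 24 / 3 = 8 ml.
- 15 draws: 15 x 4 x 3 = 180 ml; 180 - 144 = 36 ml; 36 / 144 = 25.0%. Per session, 36 / 3 = 12 ml.

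**Check of the counting method.** Protocol 5.12.4 uses two 4 ml tubes for COHb and one 4 ml tube for cotinine at each of three visits: (2 + 1) x 4 x 3 = 36 ml. The protocol states: "Approximately 36 ml of blood will be required for blood BoE assessments during the entire study". The same method reproduces that figure exactly, so tube volume times draws times visits appears to be the protocol's own convention.

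**Total study blood for a PK-subset subject.** Add the 36 ml for biomarkers and the approximately 25 ml for clinical laboratory tests (Protocol 5.12.10.3):

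- As stated: 144 + 36 + 25 = 205 ml.
- With 14 draws: 168 + 36 + 25 = 229 ml.
- With 15 draws: 180 + 36 + 25 = 241 ml.

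The subset is 12 + 12 = 24 subjects.

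**The case against.** The arithmetic and the missing draw are hard to dispute. The case on the other side concerns how much they matter.

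- *The consequence is small.* The excess is 8 to 12 ml per session in 24 of 140 subjects, for a secondary endpoint. Samples at 15 and 30 minutes bracket the missing one. This stands, and it limits the weight of the point.
- *The intended schedule is clear.* Three of the four listings agree, PK is done at a single site, and 5.12.6 promises separate collection instructions that may carry the right times. This makes a missed sample less likely. Those instructions are not available here, however, and they would not correct the volume in the protocol or resolve the conflict within it.
- *The total is only approximate.* A gap of 17% to 25% is hard to call rounding, particularly when the biomarker volume, hedged in the same way, is exact. That is a single comparison, so it supports the reading without proving how 144 was derived. The figure fits 12 draws, but the documents do not show where it came from, and no motive should be read into its direction.
- *Harm to subjects is not shown.* The consent form is not among the documents, so nothing can be said about the volume subjects were told.
- *The change is an amendment.* Protocol 10.3 and 10.4 require IRB approval of revisions. This is correct and belongs in the cost.

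**Conclusion.** The point holds. The total in Protocol 5.12.6 is wrong on that section's own inputs, by 24 ml (17% of the stated figure). It is wrong by 36 ml (25%) on the schedule that the synopsis and SAP use. The protocol also contradicts itself on whether a 20-minute sample is taken, and its cross-reference to the events tables does not settle the matter.

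This rests on 4 ml being taken at every listed time in all three sessions, as written. It does not extend to any breach of a blood-volume limit, to the consent form, or to power, alpha or the primary analysis. It should still be corrected, because it is a subject-burden figure and a draw list in operative procedures text.

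**What to change.** Insert the 20-minute sample in Protocol 5.12.6, so that it agrees with the synopsis, SAP 9.1 and the SAP 14.3 note, and restate the PK volume there as approximately 180 ml. This is the smaller edit, since three of the four listings already have 15 times. If the 20-minute sample is not wanted, delete it from those three places and state 168 ml in 5.12.6. Whichever is chosen, the separate PK collection instructions should be checked against it.

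The cost is a short protocol amendment with IRB approval and a higher stated blood volume. Neither option changes the sample size or the planned tests.
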